**Table 1. Nice categories of lifetime BC risk and subsequent management dependant on risk**

	Moderate risk (17-29%)	High risk (>30%)
Yearly screening	up to age 50	up to age 60
Chemoprevention	'consider'	'offer'
Risk reducing surgery	none	offer

\*Many referrals will be assessed at 'average' risk and returned to primary care

**Models for assessment of breast cancer risk.**

Early observations on the greater incidence of breast cancer in nuns and the increased effect on risk of older age of first birth (Ramazzini 1713, MacMahon 1970) and family history (Broca 1866, Lynch & Krush 1966) suggested that both reproductive/lifestyle and familial factors were related to risk of breast cancer (Brinton 1982). Models combining these risk factors were developed to estimate overall breast cancer risk in individuals (Gail 1989).

The Gail (1989) model includes the risk factors shown in table 2 although only a limited first degree family history is used. In our clinic the expected number of cancers compared with the number observed was 0.48 using the Gail model (Amir 2003, Evans 2014). Before 2004, we used the Claus model modified by other risk factors which gave an E/O of 1.22. After 2004 the Tyrer -Cuzick model was used which includes a larger number of risk factors, including a more extensive family history and gave an E/O of 0.81 (Tyrer 2004). Recently even greater precision has been obtained by adding more risk factors including mammographic density and breast cancer risk associated single nucleotide polymorphisms (SNPs). (Tyrer-Cuzick model v8. 2017; <http://www.ems-trials.org/riskevaluator/>).

Some models assess only family history in order to help predict the probability of a gene mutation. (Mutations are now called pathological variants [PVs]). The most widely used model to predict PVs is BOADICEA (Breast and Ovarian Analysis of Disease Incidence and Carrier Estimation Algorithm (see Table 2) (Antoniou 2004). Very recently the group in Cambridge, who developed the early BOADICEA models added hormonal/lifestyle factors and also mammographic density and SNPs to the model (Lee 2019).

**Table 2: Known risk factors and their incorporation into existing risk models. The models which depend only on family history do not predict overall risk well.**

	RR at extremes	Gail (1989)	Claus (1994)	BRCA PRO (1998)	Tyler-Cuzick V6 (2017)	BOADICEA 1 (2004)	BOADICEA V CanRisk (2019)
Prediction							
Amir et al [validation study [E/O]]		0.48	0.56	0.49	0.81		Not assessed
95% Confidence interval [30]		(0.54-0.90)	(0.59-0.99)	(0.52-0.80)	(0.85-1.41)		Not assessed
Personal information							
Age (20-70)	30	Yes	Yes	Yes	Yes	Yes	Yes
Body mass index	2	No	No	No	Yes	No	Yes
Alcohol intake (0-4 units) daily	1.24	No	No	No	No	No	Yes
Hormonal / reproductive factors							
Age of menarche	2	Yes	No	No	Yes	No	Yes
Age of first live birth	3	Yes	No	No	Yes	No	Yes
Age of menopause	4	No	No	No	Yes	No	Yes
HRT use	2	No	No	No	Yes	No	Yes
OCP use	1.24	No	No	No	No	No	Yes
Breast feeding	0.8	No	No	No	No	No	No
Plasma oestrogen	5	No	No	No	No	No	No
Personal breast disease							
Breast biopsies	2	Yes	No	No	Yes	No	No
Atypical ductal hyperplasia	3	Yes	No	No	Yes	No	No
Lobular carcinoma in-situ	4	No	No	No	Yes	No	No
Breast density	6	No	No	No	Yes	No	Yes
Family History							
First degree relatives	3	Yes	Yes	Yes	Yes	Yes	Yes
Second degree relatives	1.5	No	Yes	Yes	Yes	Yes	Yes
Third degree relatives		No	No	No	No	No	Yes
Age of onset of breast cancer	3	No	Yes	Yes	Yes	Yes	Yes
Bilateral breast cancer	3	No	No	Yes	Yes	Yes	Yes
Ovarian cancer	1.5	No	No	Yes	Yes	Yes	Yes
Male breast cancer	3-5	No	No	Yes	No	Yes	Yes

E/O Expected over observed cancer ratio (all models assessed underestimated cancer occurrence)

OCP- Oral Contraceptive.

Thus, since inception of the FHRPC, two major models have evolved. The Tyer-Cuzick model is widely used around the world. The CanRisk model evolved from the BOADICEA model (Antoniou 2004) was not published with the addition of non-family history risk factors until August 2019 but is already becoming widely used including in our own clinic (Lee 2019). In the clinics women are given their risks and are then followed up by annual mammography. The question we wish to ask in the study outlined here is how much these new models change previously given risk and should NICE guidelines be changed to include them? Most women in the clinic will have been given risk according to the early modified Claus and Tyer-Cuzick models. Our preliminary information indicates that using the new models risk can be different and thus potentially alter management according to NICE guidelines (Evans 2017. Figure 1). In addition to managing changes in NICE categories we wish to assess the psychological effects of change in risk.

### **The Tyer-Cuzick model**

The Tyer-Cuzick model was first published in 2004 (Tyer 2004) and updates were produced in 2013 (Version 7) and 2017 (Version 8). Statistically, the model is a combination of two approaches, 1) estimation from family pedigree data of the probability of carrying one or more high-risk mutations using segregation analysis, and then using the penetrance of a mutation to alter age-specific risk and, 2) regression analyses by combination of a regression model derived from case-control or cohort studies of specific relative risks combined with absolute population-based incidence rates from cancer registries (Brentnall & Cuzick 2020).

The model combines up to second degree family history and non-familial risk factors. These are family history, BRCA1 and BRCA2 in the family, age of menarche, age of first full term pregnancy, age of menopause, height, weight, use of HRT. Version 7 (2013) added Ashkenazi family history and V8 added polynomial risk scores (PRS) based on as many breast cancer risk associated SNPs that were available and mammographic density (measured either by visual analogue scale [VAS], Volpara or BIRADS). The model gives 10 year and lifetime risk until the age of 85. There is some evidence of a degree of under-prediction in women at low risk and over-prediction at high risk (Brentnall and Cuzick 2020). The risk prediction is stable for at least 19 years (Brentnall 2020). Our studies indicate the potential change in risk when adding mammographic density (Brentnall 2015, Warwick 2014), a PRS (Cuzick 2017, Evans 2017) and combining density and PRS (van Veen 2018, Brentnall 2020).

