**Figure 3. BIRADS categories (see <https://densitas.health/blog/breast-density-scales>)**

## 2. DNA measurements of risk of breast cancer

Genome wide association studies (GWAS) (Michailidou 2017, Turnbull 2010, Easton 2007, Mavaddat 2019) reported a series of common genetic variants (SNPs) each carried by 28-44% of the population associated with a 1.07-1.26 relative risk of BC. The first seven breast cancer risk associated variants were published in 2007 (Easton 2007). At the time of the initiation of the FH-Risk study (see below for explanation of FH-Risk study) in 2010, details of 18 variants were available. As a result of studies from the Breast Cancer Associated Consortium (which includes data from Manchester) a total of 313 variants are available and can be incorporated into the Tyrer-Cuzick v8 and BOADICEA V models (Mavaddat 2019). In an early report from the FH-Risk study we demonstrated that adding the results

[figure not shown]
of the 18 SNP score to the Tyrer-Cuzick model altered risk such that 25% of women increased risk and 25% decreased risk indicating the importance of SNPs in defining risk in women at moderate and high risk of breast cancer (Evans 2017).

PVs (mutations) in the TP53, BRCA1 and BRCA2 genes were shown to be associated with a high risk breast cancer in the 1990ies (Malkin 1990, Miki 1994, Wooster 1995). Since a number of potential breast cancer genes have been discovered. In order to delineate genes which are definitively related to breast cancer the Breast Cancer Association Consortium estimated the breast cancer risk association of 34 potentially important genes in 67,269 women diagnosed with breast cancer and 59,299 controls from a large number of study groups including PROCAS and FH-Risk studies from Manchester (Dorling 2020). The genes reported with PVs which were associate with a greater than twofold increase in breast cancer risk are *ATM*, *BRCA1*, *BRCA2*, *CHEK2*, *PALB2*, *BARD1*, *RAD51C*, *RAD51D* and *TP53*. **All women in the FH-Risk study have been tested for SNP313 and all potential breast cancer genes.**

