### **Risk estimation models to be used to recalculate risk**

#### ***Calculation using Tyrer-Cuzick Version 8***

Phenotypic risk will be assessed using predicted remaining 10-year and lifetime risks to age 85 from the TC model V8 (Tyrer 2004; <http://www.ems-trials.org/riskevaluator/>). The following information from the original risk questionnaire collected before 2012 will be incorporated: age at baseline; first and second-degree relatives (age affected by breast and ovarian cancer or current age or age at death); age at first child, menarche and menopause; height and weight; and history of prior benign breast disease. Changes in these risk parameters will be assessed at subsequent clinical appointments and incorporated into the model.

Version 8 of the TC Model differs from V6 in that risk is estimated until the age of 85 (from 73 or 80 years) and because breast cancer risks have generally increased since V6 was developed (Tyrer et al., 2004). Thus, women will have in any case somewhat higher risks than previously given at their initial

appointment. However they still may end up with a lower risk estimate than originally given when MD and SNPs are taken into account (Brentnall et al., 2015).

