### ***Calculation using BOADICEA V – Can-Risk***

Collaborative work with the Cambridge team that have now produced a user-friendly risk algorithm called CanRisk from their BOADICEA programme, means we can now provide bespoke breast cancer 10-year and remaining lifetime risks especially for those who carry pathogenic variants in moderate risk genes CHEK2 and ATM that are not provided for in Tyrer-Cuzick model (Archer et al 2020). CanRisk includes the same inputs as Tyrer-Cuzick (above) but also includes additional genes. Women will be provided the CanRisk output instead of Tyrer-Cuzick when they carry a pathogenic variant in any of the high or moderate risk genes. Comparisons will also be made to identify discrepancies in 10-year risks that would mean women were in different risk categories.

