#### Primary endpoints:

- 10-year and lifetime breast cancer risk and the corresponding NICE risk categories for two risk prediction models: i) TCv8 and ii) BOADICEA v5.
- Risk scores from TCv8 and BOADICEA will be assessed using different model inputs: i) classical factors alone, ii) classical factors plus mammographic density (BIRADS) and iii) classical factors plus mammographic density plus SNPs.

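### The SAP's input sets omit the gene-panel result, so the analysis cannot show how mutation testing changes risk, and no rule enters a negative result in the Tyrer-Cuzick estimate

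*Combined protocol and SAP*

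**What the plan says.** **What is promised.** The Study Summary names high- and moderate-risk gene analysis among the things the recalculation is based on. Section 1.3 (Rationale), aim iii in section 2.1 and primary objective viii of the Statistical Analysis Plan also treat gene information or mutation testing as part of the updated risk.

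**What is available.** Section 1.2 (DNA measurements of risk of breast cancer) states "All women in the FH-Risk study have been tested for SNP313 and all potential breast cancer genes". Section 3.1 (Genetic testing - Assay methods) confirms that results for a 35-gene panel are already held for every FH-Risk participant.

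**What the operative text does with it.**
- The SAP's primary endpoints define three input sets for both models. The fullest is "iii) classical factors plus mammographic density plus SNPs". Item iii of the SAP's Analysis section repeats the same three.
- Under Calculation using BOADICEA V – Can-Risk, women are "provided the CanRisk output instead of Tyrer-Cuzick when they carry a pathogenic variant in any of the high or moderate risk genes". By implication, non-carriers are given the TCv8 figure.
- Under Calculation using Tyrer-Cuzick Version 8, the listed items are age, affected relatives and "age at first child, menarche and menopause; height and weight; and history of prior benign breast disease". No gene-test result is listed.

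**How the model works.** Section 1.2 says that one of the two components of Tyrer-Cuzick is "estimation from family pedigree data of the probability of carrying one or more high-risk mutations using segregation analysis", with penetrance then applied. It lists "BRCA1 and BRCA2 in the family" among the model's factors, but does not say how a positive, negative or untested status is coded.

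**The concern.** Two things follow if the plan is carried out as written.

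First, primary objective viii includes mutation testing in the change to be measured, but no analysis step compares estimates with and without the panel result. The effect of testing on risk score or NICE category would go unreported. That includes the effect of a negative result, which can be expected to be much the commoner outcome.

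Second, the pedigree part of Tyrer-Cuzick gives each woman some probability of carrying a high-risk mutation. A negative test lowers that probability. If the TCv8 run does not take the negative result in, the estimate keeps the pre-test probability and is too high for that woman. The figure is discussed with her and, with her consent, sent to her GP (section 3.2). It helps define the increased and decreased groups in Parts 2 and 3, and it is the objective risk in Part 4. The lifetime limits of 17% and 30% in Table 1 are tied to different management.

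**Working it through.** The plan gives no figure for the effect of a negative result, so there is nothing to reproduce. The check is a comparison of the texts, followed by an illustration under stated assumptions.

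**Texts side by side**

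| Place | Gene-panel result |
|---|---|
| Study Summary; 1.3; aim iii; SAP objective viii | Part of the updated risk |
| Sections 1.2 and 3.1 | Held for all women |
| SAP primary endpoints; SAP Analysis item iii | In none of the three input sets, for either model |
| Calculation using BOADICEA V – Can-Risk | Carriers are given CanRisk; a negative result is not mentioned |
| Calculation using Tyrer-Cuzick Version 8 | Not among the listed questionnaire items |

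No passage says a negative result is entered, and none says it is left out.

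**Illustration.** Let p be the pedigree-based carrier probability before testing, F the lifetime risk in carriers, r the lifetime risk in non-carriers and s the panel's sensitivity.

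- Estimate without the panel: u = pF + (1 − p)r.
- Carrier probability after a negative panel: q = p(1 − s)/(1 − ps). Estimate with it: qF + (1 − q)r.
- With s = 100%, the overstatement is u − r = p(F − r).

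The documents give none of these values. The nearest is the 10% BRCA1/2 likelihood threshold for clinical testing in section 3.1. I assume p = 1-10%, F = 50-80% and r = 15-28%. The category limits of 17% and 30% are from Table 1.

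- Smallest overstatement: 0.01 × (50 − 28) = 0.22 points.
- Largest: 0.10 × (80 − 15) = 6.5 points.

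Estimate without the panel, in %. Bold means a higher category than r itself.

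| p | r | F = 50 | F = 60 | F = 70 | F = 80 |
|---|---|---|---|---|---|
| 2% | 15 | 15.7 | 15.9 | 16.1 | 16.3 |
| 2% | 28 | 28.44 | 28.64 | 28.84 | 29.04 |
| 5% | 15 | 16.75 | **17.25** | **17.75** | **18.25** |
| 5% | 28 | 29.1 | 29.6 | **30.1** | **30.6** |
| 10% | 15 | **18.5** | **19.5** | **20.5** | **21.5** |
| 10% | 25 | 27.5 | 28.5 | 29.5 | **30.5** |
| 10% | 28 | **30.2** | **31.2** | **32.2** | **33.2** |

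At p = 1% and 2% no category changes at any r tried (15, 20, 25 and 28%). At r = 20% none changes up to p = 10%.

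**Imperfect panel.** Take p = 10%, F = 70%, r = 28%. Without the panel the estimate is 32.2%. With s = 100% and a negative result it is 28.0%. With s = 85%, q = 0.10 × 0.15/(1 − 0.085) = 1.64%, and the estimate is 28 + 0.0164 × 42 = 28.7%. Most of the 4.2-point overstatement is still removed.

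**The case against.** The strongest reply is that this is silence rather than error, and much of that stands.

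- **The TCv8 list proves little.** It covers items from the original questionnaire and also omits density and SNPs, which certainly enter the model. The absence of a gene result there does not show that it is left out.
- **Other passages point towards use.** The Study Summary, section 1.3 and aim iii speak of gene information without limiting it to carriers. Section 3.1 says CanRisk covers additional genes and names only "CHEK2 and ATM that are not provided for in Tyrer-Cuzick model", which suggests that Tyrer-Cuzick takes some gene information already.
- **Some women may already have had a clinical test.** BRCA1/2 testing was done when clinically indicated at a likelihood of 10% or more, which is the top of the assumed range. No rule says how those results enter TCv8 either.
- **The regression of change in score is open-ended** about which risk factors it covers. But a score run without the panel result cannot change because of it.

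A reader might infer that non-carriers are definitely scored as untested, that women who test negative cannot move down, and that Part 1's counts are biased because carriers move up while others stay. The documents do not support this. No passage says that TCv8 is run as untested. In the pilot, 53 of 106 women fell by at least one category and 13 rose once density and SNPs were added. The SAP's input sets leave the panel out for carriers as well; the switch to CanRisk governs what women are given, not a described analysis. Nor can the panel be said to have excluded a mutation: its sensitivity is not stated, so a negative result lowers the probability without setting it to zero.

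None of this answers the main point. The defined input sets stop before the panel, so a primary objective that names mutation testing has no analysis step that delivers it.

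**Conclusion.** The concern holds as a gap between the objectives and the operative analysis. The effect of mutation testing on risk and NICE category cannot be obtained from the SAP's three input sets, and no rule states whether a negative result enters TCv8.

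If it does not enter, the direction of error for a woman who tested negative is upward, provided carriers have the higher risk. The size cannot be derived from the documents. The range of about 0.2 to 6.5 percentage points rests wholly on the assumed carrier probability, carrier risk and non-carrier risk, with a fully sensitive panel. At a prior probability of 1-2% it is small (at most 0.02 × (80 − 15) = 1.3 points) and matters only for women already very close to a limit. At 5-10% it is enough to move some women across 17% or 30%. How many such women the cohort holds is unknown, because no distribution of carrier probability is given, so no count of misclassified women should be quoted.

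**What to change.** 1. In the SAP's primary endpoints and in item iii of its Analysis section, add a fourth input set: classical factors, density, SNPs and the woman's own gene-panel result, negative as well as positive. Run it in each model as far as that model accepts the gene, and state which genes and which results each model can take.
2. Keep the three sets without the panel as comparators.
3. Report how many women move up and how many move down a NICE category when the panel result is added, separately for positive and negative results.
4. Reconcile the two Calculation sections of 3.1 with the Study Summary, section 1.3 and aim iii on whether a negative BRCA1/2 result enters the TCv8 run. Which figure women are given is for the investigators to settle; this point does not prescribe it.

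The cost is one more run per model, one table and protocol wording, using results already held. The documents do not describe how TCv8 codes a negative test, so that needs checking first. A possible downside is that fewer women are shown as high risk.

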### **The BOADICEA V (CanRisk) model**

The first BOADICEA model was published in 2004 based on family history alone (Antoniou 2004).

BOADICEA V extends the BOADICEA BC risk prediction model to allow for consistent prediction of personal BC for unaffected women on the basis of their rare (high risk and moderate risk) BC genetic

[figure not shown]
susceptibility variants, common genetic variants, explicit family history and other known risk factors. The model incorporates the effects of truncating variants in BRCA1, BRCA2, PALB2, CHEK2, ATM and a PRS based on 313 single-nucleotide polymorphisms (SNPs). The other risk factors included in the model are MD, age at menarche, age at menopause, parity, age at first live birth, oral contraceptive use, HRT use, height, BMI, and alcohol intake (Lee 2019). Among all factors considered, the predicted UK BC risk distribution is widest for the PRS, followed by mammographic density. The highest BC risk stratification is achieved when all genetic and lifestyle/hormonal/reproductive/anthropomorphic factors are considered jointly. With all factors, the predicted lifetime risks for women in the UK population vary from 2.8% for the 1st percentile to 30.6% for the 99th percentile, with 14.7% of women predicted to have a lifetime risk of  $\geq 17\% < 30\%$  (moderate risk according to National Institute for Health and Care Excellence [NICE] guidelines) and 1.1% a lifetime risk of  $\geq 30\%$  (high risk).

## **'New' risk factors incorporated into risk models – mammographic density & DNA tests**

### **1. Measurement of mammographic density**

[figure not shown]
The amount of dense tissue in proportion to the size of the breast, mammographic density is a strong breast cancer risk factor (figure 2). In the NIHR PROCAS (Predicting Risk of Cancer At Screening) study we assessed several methods for measuring the proportion of breast tissue in the breast in the NHS Breast Screening Programme. The importance of breast density for predicting risk is shown in figure 1. The risk of breast cancer (odds ratio) was 4 fold higher in the top quintile of density compared with the lowest. We compared five methods for density measurement: visual analogue scales (VAS), an AI method based on convolutional neural networks (CNN) and a commercial measure, Densitas. These three measures give density as an area of dense tissue compared with the area of the breast. Two other commercial measures were used which measure the volume of breast dense tissue and the volume of the breast Volpara and Quantra. The percent density assessed by our radiologists using a 0-100 visual analogue scale (VAS) was the optimal method but is cumbersome in practice. Our group has developed an automated method depending on convoluted neural networks (CNN. Ionescu 2017) which gives similar results to VAS and may be the method of choice in the future for estimating density for incorporating density into the risk models used in the clinic. The automated volumetric method, Volpara, performed well and we will also assess this method in the current study. The most widely used visual method for estimating density in breast radiology is the Breast Imaging-Reporting and Data System (BIRADS). It is a risk assessment and quality assurance tool developed by the American College of Radiology that provides a widely accepted lexicon and reporting schema for imaging of the breast. The BIRADS for density is shown in figure 3. The breast appearance is divided into four measures, (A) the breasts are almost entirely fatty, (B) there are scattered areas of fibroglandular density, (C) the breasts are heterogeneously dense, which may obscure small masses and (D) the breasts are

extremely dense, which lowers the sensitivity of the mammogram. The Tyrer-Cuzick model can use VAS, Volpara or BIRADS for risk calculation whereas BOADICEA V uses BIRADS only (T-C v8, BOADICEA V).

**Figure 2** Odds ratio of developing breast cancer by quintiles of percent density and method ([name] 2018, Ionescu 2019) (VAS – visual analogue scale. CNN – convoluted neural networks)

